### **5.10.2 Infection prophylaxis and treatment**

Participants receiving acalabrutinib are at risk for infection, and appropriate prophylaxis in accordance with institutional standards is recommended. In general, participants with documented infectious complication should receive oral or IV antibiotics or other anti-infective agents as considered appropriate by the Investigator for a given infectious condition, according to standard institutional practice.

### **5.10.3 Nausea/vomiting**

No routine prophylactic anti-emetic treatment is required at the start of treatment; however, participants should receive appropriate anti-emetic treatment at the first onset of nausea or vomiting and as required thereafter per institutional guidelines.

### **5.10.4 Diet**

Participants should maintain a normal diet unless modifications are required to manage an AE such as diarrhea, nausea or vomiting.

### **5.10.5 Gastric acid reducing agents**

Co-administration of acalabrutinib and a proton pump inhibitor should be avoided. If treatment with a gastric acid reducing agent is required, investigators should consider using a H2-receptor antagonist (e.g., ranitidine or famotidine) or an antacid (e.g., calcium carbonate).

In the case of antacids, acalabrutinib dosing should be separated by at least 2 hours. For use of H2-receptor antagonists, acalabrutinib dosing should be taken 2 hours before administration of H2-receptor antagonist.

### **5.10.6 Transfusions of platelets and red blood cells**

Platelet transfusions are permitted as medically necessary per institutional guidelines (e.g., for platelets <10,000/µL in the absence of clinical bleeding). Each transfusion event (and number of units given) will be recorded in the CRF.

Red blood cell transfusion should be considered for all participants with anemia, especially those with hemoglobin values ≤6 g/dL. Each transfusion event (and number of units given) will be recorded in the CRF.

### **5.10.7 Anti-platelet agents and anticoagulants**

Use of vitamin K antagonists (e.g., warfarin) is prohibited while on study.

Other anticoagulants (direct anticoagulants, heparin products) and antiplatelet agents may be used in participants who have controlled coagulopathy at baseline, as well as those who develop a coagulopathy on study. Participants who develop a requirement for therapeutic anticoagulation while on study (e.g., new atrial fibrillation, or venous thrombosis) may stay on study, and will be carefully monitored for bleeding risks.

### 5.10.8 Tumor Lysis Syndrome

Tumor lysis syndrome associated with CLL should be monitored (e.g., uric acid) and appropriate hydration measure and therapy with anti-hyperuricemic (e.g., allopurinol) should be performed as clinically indicated per institutional guidelines.

### 5.10.9 Study Drug Overdose

In the event of participant ingestion of more than the prescribed dosage of acalabrutinib (100 mg BID), observation for any symptomatic side effects should be instituted, and vital signs, biochemical and hematologic parameters should be followed closely (consistent with the protocol or more frequently, as needed). Appropriate supportive management to mitigate adverse effects should be initiated per institutional guidelines. If the overdose ingestion of acalabrutinib is recent and substantial, and if there are no medical contraindications, use of gastric lavage or induction of emesis may be considered. Overdoses should be reported by the Investigator to the Sponsor and AstraZeneca as described in [Section 14.4.1](#).

## 6.0 ANTICIPATED ADVERSE EVENTS

---

### 6.1 Acalabrutinib

Per the Investigator Brochure edition 9.0 dated Feb 2020 the expected toxicities for acalabrutinib are:

System Organ Class	Adverse Reactions
Infections and infestations a	
Very common	Infection b , upper respiratory tract infection, lower respiratory tract infection c , urinary tract infection
Common	Herpesvirus infection
Blood and lymphatic system disorders d	
Very common	Neutropenia e , anemia f , thrombocytopenia g , lymphocytosis h
Nervous system disorders	
Very common	Headache, dizziness
Rare	Progressive multifocal leukoencephalopathy
Gastrointestinal system disorders	
Very common	Diarrhea, nausea
Musculoskeletal and connective tissue disorders	
Very common	Musculoskeletal pain i , arthralgia
Metabolism and nutrition disorders	
Rare	Tumor lysis syndrome
General disorders and administration site conditions	
Very common	Fatigue j
Skin and subcutaneous tissue disorders	
Very common	Bruising k , rash l
Vascular disorders	
Very common	Hemorrhage m
Cardiac disorders	
Common	Atrial fibrillation or flutter, hypertension
Laboratory abnormality	
Very common	Uric acid increase, ALT increase, AST increase, bilirubin increase
Neoplasms, benign, malignant, and unspecified	

System Organ Class	Adverse Reactions
Common	Second primary malignancy, non-melanoma skin cancer
a. Includes any adverse reactions involving infection or febrile neutropenia	
b. Upper respiratory tract infection, nasopharyngitis and sinusitis	
c. Includes pneumonia, lower respiratory tract infection, bronchitis, bronchiolitis, tracheitis, and lung infection	
d. Derived from adverse reaction and laboratory data	
e. Includes neutropenia, neutrophil count decreased, and related laboratory data	
f. Includes anemia, red blood cell count decreased, and related laboratory data	
g. Includes thrombocytopenia, platelet count decreased, and related laboratory data	
h. Includes lymphocytosis, lymphocyte count increased, and related laboratory data	
i. Includes back pain, bone pain, musculoskeletal chest pain, musculoskeletal pain, musculoskeletal discomfort, myalgia, neck pain, pain in extremity and spinal pain	
j. Includes asthenia, fatigue, and lethargy	
k. Includes bruise, contusion, and ecchymosis	
l. Includes rash, dermatitis, and other related terms	
m. Includes hemorrhage, hematoma, hemoptysis, hematuria, menorrhagia, hemarthrosis, and epistaxis	

Very common ( $\geq 1/10$ ); Common ( $\geq 1/100$  to  $< 1/10$ ); Uncommon ( $\geq 1/1,000$  to  $< 1/100$ ); Rare ( $\geq 1/10,000$  to  $< 1/1,000$ ); Very rare ( $< 1/10,000$ ); not known (cannot be estimated from the available data).

The important risks of acalabrutinib are the following:

### **Hemorrhage**

Serious hemorrhagic events, including central nervous system, respiratory, and gastrointestinal hemorrhage, have been reported in clinical trials with acalabrutinib; some of these bleeding events resulted in fatal outcomes. Grade 3 or higher bleeding events, including gastrointestinal, intracranial, and epistaxis have been reported in 2% of patients. Overall, bleeding events including bruising and petechiae of any grade occurred in approximately 50% of patients with hematological malignancies.

The mechanism for hemorrhage is not well understood. Acalabrutinib may further increase the risk of hemorrhage in patients receiving antiplatelet or anticoagulant therapies and patients should be monitored for signs of bleeding. Consider the benefit-risk of withholding acalabrutinib for 3-7 days pre- and post-surgery depending on the surgery and the risk of bleeding.

### **Infections**

Serious infections (bacterial, viral or fungal), including fatal events and opportunistic infections, have been reported in clinical studies with acalabrutinib. The most frequently reported Grade 3 or 4 infection was pneumonia. Across the acalabrutinib clinical development program (including subjects treated with acalabrutinib in combination with other drugs), cases of hepatitis B virus (HBV) reactivation (resulting in liver failure and death in 1 case) and cases of progressive multifocal leukoencephalopathy have occurred in subjects with hematologic malignancies. Monitor patients for signs and symptoms of infection and treat as medically appropriate.

### **Cytopenias**

Treatment-emergent Grade 3 or 4 cytopenias including neutropenia, anemia, and thrombocytopenia have occurred in clinical studies with acalabrutinib. Subjects should be closely monitored as appropriate.

### **Second primary malignancies**

Second primary malignancies, including solid tumors and skin cancers, have been reported in patients treated with acalabrutinib. The most frequent second primary malignancy was skin cancer (basal cell carcinoma). Subjects should be monitored for signs and symptoms of malignancy. Subjects who develop a second primary malignancy

should be managed according to institutional guidelines with diagnostic evaluations as clinically indicated, and it may be necessary for subjects to permanently discontinue study treatment. Continuation of acalabrutinib treatment should be discussed with the primary investigator.

### Atrial fibrillation

Events of atrial fibrillation/flutter have been reported in clinical studies with acalabrutinib, particularly in subjects with cardiac risk factors, hypertension, diabetes mellitus, acute infections, and a previous history of atrial fibrillation. The mechanism for atrial fibrillation is not well understood.

## 7.0 DOSE DELAY / MODIFICATION GUIDELINES

### 7.1 Dose Delays

Any toxicity observed during the course of the study could be managed by an interruption of the study drug treatment. Repeat dose interruptions are allowed as required, for a maximum of 4 weeks on each occasion. Please refer to Tables 7.2.1 and 7.2.2 for dosing delays and modifications.

In general, dosing interruptions are permitted in the case of medical / surgical events or logistical reasons (i.e., elective surgery, unrelated medical events) not related to study therapy. Participants should be placed back on study therapy within 4 weeks of the scheduled interruption, unless otherwise discussed with the investigator. The reason for interruption should be documented in the participant's study record.

### 7.2 Dose Modifications

Please refer to Acalabrutinib Investigator Brochure edition 9.0^32 for dosing delays and modifications.

Unavoidable use of strong CYP3A inhibitor or inducer may also require a reduction or increase of acalabrutinib dose (refer to Table 7.2.2).

**Table 7.2.1 Recommended Dose Modifications for Adverse Reactions**

Event	AE Occurrence	Dose Modification
Grade 3 or greater non-hematologic toxicities, Grade 3 thrombocytopenia with bleeding, Grade 4 thrombocytopenia or Grade 4 neutropenia lasting longer than 7 days	1 st or 2 nd occurrence:	Interrupt acalabrutinib until resolved to Grade 1 or baseline and resume at 100 mg PO BID.
	3 rd occurrence:	Interrupt acalabrutinib until resolved to Grade 1 or baseline and resume at 100 mg PO once daily (QD)
	4 th occurrence:	Discontinue study drug. Remove participant from study

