
Autoimmune hemolytic anemia (AIHA) is a life-threatening disease with an incidence of 1-3 per 100,000 persons per year. In addition to idiopathic AIHA, a number of underlying conditions have been associated with this disorder, including viral infections, autoimmune and connective tissues diseases, and lymphoproliferative disorders. AIHA is particularly common among patients with chronic lymphocytic leukemia (CLL) with an incidence of ~2.3% as reported in a recent retrospective analysis of 1750 patients. First-line therapy of AIHA typically consists of corticosteroids, which induce initial responses in 70%-85% of patients with warm AIHA; however, only one-third of patients remain in long-term remission after stopping corticosteroids, and a further 50% require maintenance doses. Subsequent lines of immunosuppressive therapy carry initial response rates from 40-60%, though relapses are similarly common. Therefore, in the relapsed/refractory setting, safe and effective treatments for AIHA are needed. Ibrutinib, a small molecule inhibitor of Bruton tyrosine kinase (BTK), inhibits B-cell activity and has been shown to inhibit production of auto-antibodies in murine models of autoimmunity, suggesting their potential efficacy in multiple autoimmune conditions. Preliminary evidence suggests that ibrutinib may be efficacious in treatment of CLL-associated AIHA, as 50% of patients who presented with hemolysis and received therapy with the BTK inhibitor were able to discontinue immunosuppressive therapy. A second-generation selective BTK inhibitor, acalabrutinib, may be associated with fewer off-target effects including diminished frequency of side effects including bleeding and atrial fibrillation, and showed increased efficacy against AIHA in a murine model. This study will assess if acalabrutinib can increase hemoglobin and reduce transfusion requirements in patients with relapsed or refractory AIHA.
	
Treatment Description	

Eligible participants enrolled in this study will receive acalabrutinib (100 mg, PO BID) for 12 cycles. Participants that experience disease progression or unacceptable toxicities will discontinue study drug and be removed from study. Treatment with acalabrutinib may be continued beyond 12 cycles, for a maximum of 36 cycles, if the study participant might benefit from ongoing therapy in the opinion of treating physician (e.g., ongoing therapy for CLL is required).
	
Objectives	

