## 5.6 Duration of Therapy and Criteria for Removal from Protocol Therapy

Participants will receive protocol therapy until one of the below criteria are met:

- Completed protocol therapy (see [Section 5.3](#))
- AIHA relapse or progressive disease for CLL
- Participant is deemed intolerant to protocol therapy because of toxicity, despite dose modification/delay
- General or specific changes in the patient's condition which render the patient unacceptable for further treatment in the judgment of the investigator
- Withdrawal of consent for further protocol therapy (See [Section 17.5](#))

Once participants meet criteria for removal from protocol therapy, the participant should then proceed to End of Treatment assessments, and then to follow-up (Refer to the Follow-Up section below).

Documentation of the reason for discontinuing protocol therapy and the date effective should be made in the Electronic Health Record/medical record and appropriate eCRF.

The COH DCC and the Study PI should be promptly notified of the change in participant status.

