## 5.7 Follow-Up

All participants will enter follow-up after completing End of Treatment assessments (per Study Calendar in [Section 10.0](#) footnote d), until one of criteria in Section 5.8 below is met.

Assessment time points and windows are detailed in [Section 10.0](#).

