### 11.2 Secondary Endpoint(s)

Objective	Endpoint	Start	End
Evaluate acalabrutinib's ability to induce short term and sustained hemoglobin response	AIHA ORR after 3 and 12 cycles	First dose of study drug [i.e., C1 Day 1]	After 12 cycles of treatment
	Frequency of PRBC transfusion while receiving acalabrutinib		Up to 30 days after last dose
	AIHA-specific Relapse-Free Survival (RFS)		Until time of AIHA relapse, death, or end of follow-up, whichever occurs first. [up to 12 months after the last dose of study drug]
	AIHA Sustained Response		
Assess the toxicity of acalabrutinib	Incidence and type of treatment-related toxicity [per CTCAE v5.0 and IWCLL 2018 criteria  ]		Up to 30 days after last dose of study drug
Evaluate efficacy of acalabrutinib in CLL	CLL ORR after 6, 12 cycles, per standard IWCLL criteria	First dose of study drug [i.e., C1 Day 1]	After 6 or 12 cycles from treatment start
	CLL-specific event-free survival (EFS)		Until time of progression, death, start of new therapy, or end of follow-up, whichever occurs first. [up to 12 months after the last dose of study drug]
	Duration of CLL response	When CR/PR is first documented	

AIHA ORR after 3 and 12 cycles: it will be defined as the proportion of patients achieving AIHA CR/PR after 3 or 12 cycles respectively. Patients evaluable for this endpoint include: 1) those who receive at least 3 or 12 cycles of acalabrutinib treatment and have AIHA response evaluation after 3 or 12 cycles; 2) patients

who terminate acalabrutinib prior to completing 3 or 12 cycles due to relapse of AIHA or CLL progressive disease (they will be counted as non-responders).

Frequency of PRBC transfusion: it will be defined as the number of PRBC transfusions from start of protocol treatment through EOT.

*AIHA-specific Relapse-Free Survival (RFS):* it will be defined as the time from start of acalabrutinib treatment until death, or relapse of AIHA. Patients without death, or AIHA relapse will be censored at the last follow-up or when they begin new therapy for CLL or AIHA. **Relapse of AIHA will be determined by the investigator. A minimal requirement is Hgb<10 g/dL and evidence of hemolysis per laboratory parameters.** Investigators will document the criteria by which relapse was assessed.

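### The synopsis and Table 7.2.1 take some participants off study when drug stops, while Sections 5.6 to 5.8 keep them in follow-up, which exposes secondary time-to-event and late-safety data to selective loss

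*Combined protocol and SAP*

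**What the plan says.** **Off study.** The synopsis, under Treatment Description, states: "Participants that experience disease progression or unacceptable toxicities will discontinue study drug and be removed from study". Table 7.2.1, at the fourth occurrence of the listed toxicities, states: "Discontinue study drug. Remove participant from study".

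**Off treatment, still on study.** Section 5.6 lists criteria for leaving protocol therapy. They include "AIHA relapse or progressive disease for CLL" and "Participant is deemed intolerant to protocol therapy because of toxicity, despite dose modification/delay". The consequence given there is that "the participant should then proceed to End of Treatment assessments, and then to follow-up". Section 5.7 makes this general: "All participants will enter follow-up after completing End of Treatment assessments". Sections 5.1, 5.3 and 5.8 set follow-up at 12 months after the last dose. Sections 5.1 and 5.8 end it earlier if new AIHA or CLL therapy starts. Section 5.8 does not name progression or toxicity as ending participation, although it allows investigator discretion on safety grounds. Study calendar footnote d requires the EOT visit after any permanent discontinuation, progression included.

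**What hangs on study status.** AIHA relapse-free survival (RFS), AIHA sustained response, CLL event-free survival (EFS) and CLL response duration run up to 12 months after the last dose (Section 11.2) and are censored at last follow-up. For RFS: "Patients without death, or AIHA relapse will be censored at the last follow-up". In Table 14.5, the last reporting window, for related serious adverse events, closes at removal from study. Section 12.5 rules out imputation.

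**The concern.** Leaving treatment and leaving the study are different events, and the plan uses both terms for the same participants. A site working from the dose-modification table could record a participant as off study when drug is stopped, and could cite investigator discretion in Section 5.8 in support. Follow-up would then end because of what happened to the participant, either toxicity or progression of one of the two diseases. Kaplan-Meier estimates assume that those censored have the same later risk as those still followed. That is hard to defend when toxicity or the other disease's relapse caused the censoring. With 22 participants, each one lost is 1/22 = 4.5% of the sample.

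**Working it through.** **The plan's own figures.** The exact binomial rule of 10 or more responders in 20 has one-sided type I error 0.04796 at a response rate of 0.3 and power 0.8725 at 0.6. These reproduce the stated 0.048 and 87%. This point does not depend on them, and no design figure changes under either reading.

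**Step 1: what triggers removal from study.** Table 7.2.1 acts only on toxicity, and only at the fourth listed occurrence. Progression, and unacceptable toxicity more broadly, come from the synopsis sentence alone. Section 5.6 covers the same situations and leads to EOT and follow-up instead.

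**Step 2: effect on each endpoint if removal is taken literally.**

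| Reason for removal | Already counted | Would be missed |
|---|---|---|
| Toxicity | None of the four endpoints | Later AIHA relapse, CLL progression, death and new CLL therapy; all four endpoints censored at removal |
| AIHA relapse | RFS and sustained-response event | Later CLL progression, new CLL therapy and death, for EFS and CLL response duration |
| CLL progression | EFS and CLL response-duration event | Later AIHA relapse and death, for RFS and sustained response |

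Start of new CLL therapy is an event for EFS and CLL response duration (Section 11.2). Under Sections 5.7 and 5.8 it would be observed and counted, and would then end participation. A participant already off study for toxicity or AIHA relapse who later starts CLL therapy would be censored instead. For RFS and sustained response, new therapy is a censoring point under either reading.

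**Step 3: primary endpoint.** Section 11.1 counts those who stop before completing 6 cycles for AIHA or CLL progression as non-responders. Those who stop that early for toxicity alone are outside the evaluable definition. Neither rule depends on later follow-up.

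**Step 4: safety windows.** The toxicity endpoint runs to 30 days after the last dose. Reporting of all serious adverse events runs to 90 days after treatment stops, or 30 days if new anticancer therapy begins. Both are counted from the end of treatment, not of study. The window tied to study removal is the later one for related serious events. Section 14.4 also collects adverse events until participation ends, although it specifies routine cycle-by-cycle recording only through EOT.

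**Step 5: upper bound on lost follow-up.** Inputs are 22 participants (Section 12.2) and at most 12 months each (Section 5.8). The share removed is not in the documents; 10% to 40% is assumed.

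- Maximum post-treatment follow-up: 22 × 12 = 264 person-months.
- 10% removed: 22 × 0.10 = 2.2, so 2; 2 × 12 = 24; 24/264 = 9%.
- 20%: 4 removed; 48/264 = 18%.
- 30%: 7 removed; 84/264 = 32%.
- 40%: 22 × 0.40 = 8.8, so 9; 9 × 12 = 108; 108/264 = 41%.

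Each figure is a ceiling, because new AIHA or CLL therapy would end some of this follow-up under Sections 5.1 and 5.8 as well.

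**The case against.** The best answer is that the operative text already settles the matter. Sections 5.1, 5.3, 5.6, 5.7 and 5.8 and calendar footnote d agree, against one synopsis sentence and one cell of a table headed as recommendations. Most sites would probably follow Section 5, so loss is possible rather than certain. That limits the severity but does not remove the conflict, because the dose table is what a site consults when toxicity recurs.

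Four stronger readings are tempting, and the documents do not support them:

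- **No EOT visit after removal.** Footnote d requires one after any permanent discontinuation.
- **Removal at progression makes every time-to-event endpoint's censoring informative.** Progression of the same disease is itself the event, so only the other disease's endpoints are exposed.
- **Adverse event follow-up stops for those with the worst toxicity.** The 30-day and 90-day windows stand regardless of study status, and Table 14.5's note requires expedited events to be followed until resolved, stabilized or irreversible.
- **Each removal loses a full 12 months.** Participants with relapsed or refractory AIHA who stop drug may soon start new therapy, which ends follow-up anyway. Rewording would not recover that time.

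The exposed efficacy endpoints are also secondary Kaplan-Meier estimates with no planned hypothesis test (Section 12.4.2).

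**Conclusion.** The contradiction is real and worth correcting, but its reach is limited. It exposes four secondary time-to-event endpoints after toxicity removal, cross-disease events after progression, new CLL therapy as an event for EFS and CLL response duration, and late reporting of related serious adverse events. A reader might infer that the trial's main result is at risk; Section 11.1 shows that it is not.

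The 9% to 41% ceiling on lost person-months rests on the assumed removal share, on every removed participant otherwise completing 12 months, and on sites applying the synopsis or table literally. The true loss could be well below this, and would be nil if all sites follow Section 5. The direction of bias cannot be calculated from the documents. If those removed have a higher later risk than those still followed, the Kaplan-Meier estimates would be too favourable.

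**What to change.** Reconcile the synopsis sentence and the fourth-occurrence cell of Table 7.2.1 with Sections 5.6 to 5.8 and footnote d. In both places, replace the removal-from-study wording with: removed from protocol therapy; proceed to EOT and follow-up per Sections 5.6 to 5.8. This changes study status and data collection only. It does not alter when drug is interrupted, reduced or stopped.

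The cost is two wording changes in an amendment. The follow-up is already specified, and footnote e describes its assessments as standard of care, so no new visits are added. The documents give no budget, so nothing is claimed about funding.
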